4.7. Safety Analyses

The primary safety endpoint will be the proportion of participants that experience one or more device-related adverse events. For corrected distance visual acuity, the proportion of participants with an improvement of more than two lines (11 or more letters), a worsening of more than two lines and a change of two lines or less will be summarized along with the exact 95% confidence interval at each visit. Biomicroscopy

results will also be presented as the proportion of participants with a clinically significant change from Baseline at each visit. Particular attention will be paid to any changes to the corneal surface. Summaries will be provided of the proportion of participants that experienced an unexpected device-related serious adverse event, the proportion of participants that experienced any adverse event and the proportion of participants that experienced each unique adverse event.

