6. ADVERSE EVENTS AND SERIOUS ADVERSE EVENTS

6.1. Definitions

Adverse Event (AE): An adverse event is defined as any untoward medical occurrence, unintended disease or injury, or any untoward clinical signs (including an abnormal laboratory finding) in participants, users or other persons whether or not related to the investigational medical device. This includes events related to the investigational device or any procedures involved (any procedure in the study protocol). For users or other persons this is restricted to events related to the investigational medical device.

Serious Adverse Event (SAE): An AE should be classified as an SAE and reported as such if it meets one or more of the following criteria:

- It results in death (i.e., the AE actually causes or leads to death);
- It is life threatening (i.e., the AE places the participant at immediate risk of death);
- It requires or prolongs inpatient hospitalization. If a participant is hospitalized to undergo a medical or surgical procedure as a result of an AE, the event responsible for the procedure, not the procedure itself, should be recorded as the event. For example, if a participant is hospitalized to undergo coronary bypass surgery, the heart condition that necessitated the bypass should be recorded. Hospitalizations for diagnostic or elective surgical procedures or hospitalizations required to allow outcome measurement for the study should not be recorded as SAEs:

- It results in persistent or significant disability/incapacity (i.e., the AE results in substantial disruption of the participant's ability to conduct normal life functions);
- It results in a congenital anomaly/birth defect in a neonate/infant born to a mother exposed to the investigational device;
- It is considered a significant medical event by the investigator based on medical judgment (e.g. may jeopardize the participant or may require medical/surgical intervention to prevent one of the outcomes listed above);
- It is considered sight-threatening by the investigator.

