6.3. Classification

6.3.1. Intensity / Severity

All adverse events should be graded on a 4 point scale (mild, moderate, marked, severe) for intensity / severity. These definitions are as follows:

- **Mild:** Transient discomfort; no medical intervention / therapy required and does not interfere with daily activities.
- **Moderate:** Low level of discomfort or concern with mild to moderate limitation in daily activities; some assistance may be needed; minimal or no medical intervention/therapy required.
- **Marked:** Considerable discomfort with limitation in daily activities; some assistance usually required; medical intervention/therapy usually required.
- **Severe:** Extreme discomfort and limitation in daily activities; significant assistance required; **significant** medical intervention/therapy required.

Note: There is a distinction between the severity and the seriousness of an adverse event. Severity is a measurement of intensity; thus, a severe reaction is not necessarily a serious adverse event (SAE). For example, a headache may be severe in intensity, but would not be serious unless it met one of the criteria for serious adverse events.

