6.3.2. Expectedness

All AEs should be evaluated as to whether they are expected or unexpected.

- **Expected (anticipated):** An adverse event is expected when the nature, severity or degree of incidence was previously described.
- **Unexpected (unanticipated):** An adverse event is unexpected when the nature, severity or degree of incidence was not previously described.

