6.4. Anticipated Adverse Events

The following is a list of anticipated adverse events:

- Ocular discomfort or irritation
- Conjunctival injection
- Canaliculitis
- Subconjunctival hemorrhage
- Punctal stenosis
- Eyelid telangiectasia
- Eyelid edema

- Eyelid induration
- Eyelid erythema
- Epiphora
- Clinically significant decrease (>10 letters) in Corrected Distance Visual Acuity
- Clinically significant increase in corneal epithelial staining, e.g., an increase in corneal staining score of 2 or more in at least one corneal region or an increase in the sum for all corneal regions of 4 or more (using NEI grid and scale)

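### The only safety summary in section 4.7 that uses seriousness is limited to unexpected, device-related events, so other serious events need not be shown as serious

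*Protocol*

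**What the plan says.** Protocol section 4.7 (Safety Analyses) lists what will be summarised. The primary endpoint is set out first: "The primary safety endpoint will be the proportion of participants that experience one or more device-related adverse events". Acuity change categories and clinically significant biomicroscopy changes follow, by visit. For adverse events beyond the primary endpoint, the section states: "Summaries will be provided of the proportion of participants that experienced an unexpected device-related serious adverse event", together with "the proportion of participants that experienced any adverse event and the proportion of participants that experienced each unique adverse event".

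Section 6.1 defines the serious event without reference to expectedness or relatedness: "An AE should be classified as an SAE and reported as such if it meets one or more of the following criteria". The criteria are outcomes, and one is specific to the eye: "It is considered sight-threatening by the investigator".

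Section 6.3.2 has every adverse event rated for expectedness. On one side, "An adverse event is expected when the nature, severity or degree of incidence was previously described". The unexpected category has the same wording with a negation, including the same use of the word or. Section 6.4 lists the anticipated events. Canaliculitis appears by name only, while acuity loss has a threshold: "Clinically significant decrease (>10 letters) in Corrected Distance Visual Acuity".

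**The concern.** The stated objective of the study (section 2) covers safety as well as effectiveness, and a reader of the report will look for the number of participants with a serious event. Section 4.7 does not leave that count open. It specifies a serious-event summary and places two further conditions on it: the event must be unexpected and it must be device-related.

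Unexpectedness is a natural condition for notifying unanticipated device effects, which section 6.1 defines separately. It is a poor sole basis for describing serious harm, because a serious event is no less serious for having been foreseen. A report that followed 4.7 as written could truthfully give zero in its only serious-event line although a device-related serious event had occurred.

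**Working it through.** The protocol gives no figure to reproduce here. The check sets the sections side by side and adds one illustrative calculation.

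**Step 1. Which stated summaries use seriousness?** From section 4.7:

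- Primary safety endpoint (device-related events): not split by seriousness.
- Acuity categories and biomicroscopy change: measurements, not split by seriousness.
- Unexpected device-related SAEs: uses seriousness.
- Participants with any event, and participants with each distinct event: not split by seriousness.

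One summary uses it. Elsewhere, section 7.4.5 requires SAE notifications to be kept as records, and section 4.8 says only that a final report will be prepared. Neither plans an SAE summary.

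**Step 2. Where does each kind of SAE appear?** Cross expectedness (6.3.2) with relatedness (6.3.3):

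| SAE is | Device-related | Not device-related |
|---|---|---|
| Unexpected | Shown as serious | Counted among any and distinct events only |
| Expected | Counted in the primary endpoint and among any and distinct events only | Counted among any and distinct events only |

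Three of the four cells have no stated summary that identifies the event as serious.

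**Step 3. Is the boundary of the one SAE summary clear?** Section 6.3.2 uses three attributes: nature, severity and incidence. Read literally, an event is expected if at least one was described beforehand, and unexpected if at least one was not. There are 2 × 2 × 2 = 8 patterns of described and not described:

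- all three described: expected only (1 pattern);
- none described: unexpected only (1 pattern);
- mixed: meets both definitions (8 − 2 = 6 patterns).

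Canaliculitis is named in section 6.4 without a severity. A sight-threatening case therefore has a described nature and, on that list alone, an undescribed severity. It meets both definitions. The text does not settle whether it enters the SAE summary.

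**Step 4. Illustration of size.** Assume all 13 participants allowed by section 3.3 receive the device and one has a device-related SAE that is judged expected.

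- Observed proportion: 1/13 = 7.7%.
- Exact (Clopper-Pearson) lower limit, solving 1 − (1 − p)^13 = 0.025: p = 1 − 0.975^(1/13) = 0.0019, or 0.2%.
- Exact upper limit, solving (1 − p)^13 + 13p(1 − p)^12 = 0.025: at p = 0.360 the left side is 0.0030 + 0.0221 = 0.0251, so the limit is 36.0%.
- Entry in the only SAE summary: 0/13 = 0%.

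The single event is hypothetical. The protocol gives no expected SAE rate.

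**The case against.** The strongest reply is that this is an omission, and one that an analysis plan commonly fills. Section 4.7 does not call its list exhaustive, and an SAP that is not shown could add a table of all SAEs. Serious events must be recorded as such under section 6, and with at most 13 participants each would probably be described individually. This stands as a limit on the weight. It does not remove the point, because the protocol itself specifies the serious-event summary and restricts it. An SAP that followed 4.7 exactly would reproduce the gap.

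Several stronger readings are tempting, and the document does not support them:

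- A reader might infer that any event type listed in 6.4 can never be shown as serious. Step 3 shows otherwise: such an event can be unexpected in severity or incidence.
- A reader might infer that these events vanish or are indistinguishable from mild irritation. In the primary endpoint they do count alike, but canaliculitis would have its own row in the summary of distinct events. Acuity worsening of more than two lines and biomicroscopy changes, with emphasis on the cornea, have their own summaries in 4.7.
- A reader might infer that the listed events are the ones most likely to be serious. The protocol does not say so. Section 1.3 reports no canaliculitis in the previous pilot study, in which 74 participants were treated.
- Section 6.3.1 requires a grade ("All adverse events should be graded on a 4 point scale (mild, moderate, marked, severe) for intensity / severity") that enters no stated summary. Tabulation by severity is routine SAP content, so its absence here is not a finding on its own.

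**Conclusion.** The point holds in limited form. Among the summaries stated in section 4.7, only unexpected device-related SAEs are identified as serious. Expected device-related SAEs and all unrelated SAEs are counted without that identification, although they remain on record as SAEs. For events of an anticipated type, inclusion in the one SAE summary turns on definitions that overlap.

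In the illustration, a device-related SAE proportion of 7.7% (exact 95% CI 0.2% to 36.0%) could stand beside 0 of 13 in the only SAE line. That rests on three assumptions: 13 treated participants, one such event, and a judgement that it was expected. It also assumes that the report contains no SAE table beyond those that 4.7 names.

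The text does not support a reading that the plan suppresses serious events or that it redefines seriousness. The weight is minor to moderate: the study is a descriptive pilot with no hypothesis, but the clause bears directly on its safety objective.

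**What to change.** In section 4.7, replace the serious-event clause with three nested counts, each given as the number and proportion of participants:

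1. with any SAE;
2. with any device-related SAE, regardless of expectedness;
3. as a subset of the second, with an unexpected device-related SAE.

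The first two counts do not depend on section 6.3.2, so they hold however the overlap is read. For the third to be reproducible, 6.3.2 should also be reworded so that no event can be both expected and unexpected.

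No new data are needed, because seriousness, relatedness and expectedness are already to be assessed for each event. The cost is an edit to the text, one or two more table lines and a safety table that may look less favourable.

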4.8. Final Clinical Report

A final clinical study report will be prepared after completion of the study.

5. DATA MANAGEMENT

Standardized CRFs will be used for reporting the results of the study. All data from the study will be entered from the CRFs into a central database. Study participants will be identified on the CRFs and in the database using the participant ID to maintain confidentiality. Incoming data will be reviewed to identify inconsistent or missing data and any adverse events. Any data issues are to be promptly addressed by the investigator.

6. ADVERSE EVENTS AND SERIOUS ADVERSE EVENTS

6.1. Definitions

Adverse Event (AE): An adverse event is defined as any untoward medical occurrence, unintended disease or injury, or any untoward clinical signs (including an abnormal laboratory finding) in participants, users or other persons whether or not related to the investigational medical device. This includes events related to the investigational device or any procedures involved (any procedure in the study protocol). For users or other persons this is restricted to events related to the investigational medical device.

Serious Adverse Event (SAE): An AE should be classified as an SAE and reported as such if it meets one or more of the following criteria:

- It results in death (i.e., the AE actually causes or leads to death);
- It is life threatening (i.e., the AE places the participant at immediate risk of death);
- It requires or prolongs inpatient hospitalization. If a participant is hospitalized to undergo a medical or surgical procedure as a result of an AE, the event responsible for the procedure, not the procedure itself, should be recorded as the event. For example, if a participant is hospitalized to undergo coronary bypass surgery, the heart condition that necessitated the bypass should be recorded. Hospitalizations for diagnostic or elective surgical procedures or hospitalizations required to allow outcome measurement for the study should not be recorded as SAEs:

- It results in persistent or significant disability/incapacity (i.e., the AE results in substantial disruption of the participant's ability to conduct normal life functions);
- It results in a congenital anomaly/birth defect in a neonate/infant born to a mother exposed to the investigational device;
- It is considered a significant medical event by the investigator based on medical judgment (e.g. may jeopardize the participant or may require medical/surgical intervention to prevent one of the outcomes listed above);
- It is considered sight-threatening by the investigator.

Unanticipated Adverse Device Effect (UADE): An unanticipated adverse device effect (UADE) is any serious adverse effect on health or safety or any life-threatening problem or death caused by or associated with a device if that effect, problem or death was not previously identified in nature, severity or degree of incidence in the informed consent form. UADEs also include any unanticipated sight-threatening events and any other unanticipated serious problem associated with a device that relates to the rights, safety or welfare of participants.

6.2. Adverse Event Assessment and Documentation

All participants who have been exposed to application of the study device should be evaluated for adverse events. All adverse events, regardless of severity and whether or not they are ascribed to the study device, should be recorded in the source documents and CRFs using standard medical terminology.

All adverse events should be evaluated beginning with onset and evaluation should continue until resolution is noted or until the investigator determines that the participant's condition is stable. The investigator should take appropriate and necessary therapeutic measures required for resolution of the adverse event. Any medication necessary for the treatment of an adverse event must be recorded on the concomitant medication CRF.

Pre-existing conditions or diseases that are chronic but stable should not be recorded on AE pages of the CRF but should be recorded in the medical history. Changes in a chronic condition or disease that are consistent with natural disease progression do not need to be recorded as adverse events and should not be recorded on the AE pages of the CRF. Clinical study staff should start assessing participants for AEs from the time of the first device application.

Whenever possible, recognized medical terms should be used when recording AEs. Colloquialisms and/or abbreviations should not be used. Only one medical concept, preferably a diagnosis instead of individual symptoms, should be recorded as the event. If more than one distinct adverse event occurs, each event should be recorded separately. However, if a constellation of signs and/or symptoms cannot be medically characterized as a single diagnosis or syndrome at the time of reporting, each individual event should be recorded as a separate AE. A diagnosis that is subsequently established should be reported as follow-up information. However, signs and symptoms that are considered unrelated to an encountered syndrome or disease should

be recorded as individual AEs (e.g. if congestive heart failure and severe headache are observed at the same time, each event should be recorded as an individual AE).

Adverse events occurring secondary to other events (e.g. sequelae) should be identified by the primary cause. A "primary" event, if clearly identifiable, should represent the most accurate clinical term to record as the AE event term. For example: Orthostatic hypotension \Rightarrow fainting and fall to floor \Rightarrow head trauma \Rightarrow neck pain. The primary event is orthostatic hypotension and the sequelae are head trauma and neck pain.

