1. INTRODUCTION

1.1. Background

The 1995 National Eye Institute (NEI)/Industry Dry Eye Workshop defined dry eye disease (DED) as a multifactorial disease of the tears and ocular surface that results in symptoms of discomfort, visual disturbance, and tear instability with potential damage to the ocular surface. Dry eye disease has a complex pathophysiology and a multifactorial etiology related to an inadequacy of one or more layers of the tear film. It is accompanied by increased osmolarity of the tears and inflammation of the ocular surface.¹ An estimated 25 million Americans are reported to have DED,² one of the most common reasons patients seek care with their eye care professional.³

DED has multiple causes and consequences, ranging in severity from mild discomfort and pain to a decrement in visual acuity resulting from irregularities in the corneal surface. Signs of DED include reduced tear volume, delayed tear clearance, abnormal tear osmolarity, decreased tear breakup time, punctate keratitis and distorted mires on keratometry or corneal topography. Symptoms include dryness, grittiness, burning, stinging, discomfort, photophobia, redness, tearing, reduced ability for prolonged reading or computer work, and fluctuating vision. These symptoms are typically worse later in the day and can be triggered or exacerbated by environmental conditions such as low humidity.

The severity and prevalence of DED in the general population increases with age and is particularly common in post-menopausal women and in those age 65 and older. While patients with mild to moderate dry eye experience a range of complaints, as described above, patients with severe dry eye are at risk for more serious ocular findings, such as punctate keratopathy evidenced by significant fluorescein staining of the cornea. More severely affected patients can experience a quality of life deficiency comparable to that of moderate to severe angina.⁴ Studies suggest that dry eye is associated with significant impact on visual function, including reading and driving⁵ as well as daily activities, social and physical functioning, workplace productivity and quality of life.⁶

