3.2.2. Safety Endpoints

The primary safety endpoint will be the proportion of participants that experience one or more device-related adverse events (e.g., irritation, conjunctival injection, epiphora, subconjunctival hemorrhage, canaliculitis, punctal stenosis, eyelid telangiectasia, eyelid edema, eyelid induration, eyelid erythema).

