If visual acuity is so poor that the participant cannot read any of the largest letters at 1 meter (i.e., the number of letters read correctly at 1 meter is zero), light perception should be tested with an indirect ophthalmoscope in a darkened room. The indirect ophthalmoscope light should be in focus at 3 feet with the rheostat set at maximum voltage. From a distance of 3 feet, the beam should be directed in and out of the eye at least four times and the participant should be asked to respond when s/he sees the light. If the examiner is convinced that the participant perceives the light, vision should be recorded as “light perception,” and, if not, vision should be recorded as “no light perception.”

Corrected Distance Visual Acuity Scoring Instructions

The ETDRS visual acuity worksheets are for clinic use only. The examiner records each letter identified correctly by circling the corresponding letter on the appropriate worksheet. The examiner records letters read incorrectly with an ‘X’ and leaves letters for which the participant makes no guesses unmarked. Each letter read correctly is scored as one point. After testing is completed, the score for each line (which is zero if no letters are read correctly) and the total score for each eye are recorded on the visual acuity worksheet. If testing at 1 meter is not required, 30 points are automatically scored for the 1-meter test. The total combined score (i.e., the sum of the 4- and 1-meter scores) are entered on the worksheet as the final visual acuity letter score.

Note: A clinically significant visual acuity decrease (defined as an increase of 0.22 or greater in logMAR score from Day 0) at a Follow-up visit will be considered an adverse event.

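### The natural-progression exemption in section 6.2 has no exception for dry eye disease, so some device-related events could be left off the AE pages before relatedness is graded

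*Protocol*

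**What the plan says.** Section 6.2 contains two recording rules. The general rule is inclusive: "All adverse events, regardless of severity and whether or not they are ascribed to the study device, should be recorded". Later in the same section comes the exemption: "Changes in a chronic condition or disease that are consistent with natural disease progression do not need to be recorded as adverse events and should" be kept off the AE pages of the CRF. The second half of that sentence is a prohibition, not an option. Nothing in it excludes the study disease or the study eyes.

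The primary safety endpoint in 3.2.2 is the proportion of participants with at least one of the "device-related adverse events (e.g., irritation, conjunctival injection, epiphora, subconjunctival hemorrhage, canaliculitis" and five further eyelid or punctal examples, ten in all). Section 6.4 lists the same ten kinds of event as anticipated AEs and adds two with numerical thresholds: an acuity loss of more than 10 letters, and the item beginning "Clinically significant increase in corneal epithelial staining, e.g., an increase in corneal staining score of 2 or more in at least one corneal region". Section 9.2.2 says that an acuity loss of 0.22 logMAR or more from Day 0 "at a Follow-up visit will be considered an adverse event", without qualification.

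On the disease itself, section 1.1 says: "Symptoms include dryness, grittiness, burning, stinging, discomfort, photophobia, redness, tearing, reduced ability for prolonged reading or computer work, and fluctuating vision". It also names punctate keratitis as a sign and reduced visual acuity as a possible consequence.

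Section 6.3.3 grades relatedness once an AE exists. Underlying illness is one ground there for Not related. An event for which underlying disease is only one plausible explanation can still be Possibly related. Section 3.6 says that the participant is masked and does not say that the investigator is.

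**The concern.** An exemption for stable or slowly progressing comorbidities is ordinary. Here it also reaches the disease under study, in the eyes under study. For signs that dry eye and the device could both produce, it asks the investigator to settle the cause before anything is written on the AE page. Section 6.3.3 is where that judgement belongs, with a grade and a record.

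An event omitted at this stage has no relatedness grade. It cannot enter the primary safety proportion, nor the any-AE and each-unique-AE summaries in section 4.7. Any error of this kind lowers the device-related count. Another instruction in 6.2, to record a diagnosis in preference to individual symptoms, adds to the risk: irritation, redness and staining could be combined as worsening dry eye, which the exemption then keeps off the page.

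**Working it through.** **1. Overlap between the endpoint and the disease**

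| Event | Listed in | Counterpart in 1.1 |
|---|---|---|
| Irritation | 3.2.2, 6.4 | Discomfort, grittiness, burning |
| Conjunctival injection | 3.2.2, 6.4 | Redness |
| Epiphora | 3.2.2, 6.4 | Tearing |
| Increased corneal staining | 6.4 only | Punctate keratitis |
| Acuity loss | 6.4 and 9.2.2 only | Reduced or fluctuating vision |
| Subconjunctival hemorrhage, canaliculitis, punctal stenosis, eyelid telangiectasia, edema, induration, erythema | 3.2.2, 6.4 | None |

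The overlap is 3 of the 10 examples in 3.2.2, and 3 + 2 = 5 of the 12 items in 6.4.

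**2. Which rule prevails**

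Take a device eye whose staining rises by 2 in one region by Day 42. Under 6.4 and the record-all sentence it is an AE, to be graded under 6.3.3. Under the exemption, if judged consistent with dry eye progression, it stays off the AE page. For acuity, 9.2.2 makes the loss an AE outright, while the exemption could still be read to remove it. No section ranks these rules, so two investigators could each follow the protocol and record different things.

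**3. What one participant is worth**

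The protocol gives no expected AE rate and no sample-size calculation (4.1), so there is no planned figure to reproduce. Inputs: at most 13 participants (3.3), with a goal of 10 completing (synopsis).

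- 1/13 = 7.7 percentage points; 1/10 = 10 percentage points.
- Exact (Clopper-Pearson) 95% intervals at n = 13: 2/13 = 15.4% (1.9 to 45.4); 1/13 = 7.7% (0.2 to 36.0); 0/13 = 0% (0 to 24.7).
- At n = 10: 2/10 = 20.0% (2.5 to 55.6); 1/10 = 10.0% (0.3 to 44.5); 0/10 = 0% (0 to 30.8).

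The counts are illustrative.

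**4. Sensitivity under assumed values**

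Let p be the true proportion of participants with a device-related AE, f the share of those whose only such events resemble dry eye, and q the probability that the exemption is applied to them. None of the three is in the protocol. The expected observed proportion is p × (1 − f × q), and the chance of observing no affected participant among 13 is (1 − that proportion)^13.

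| p | f | q | Expected observed | P(0 of 13) |
|---|---|---|---|---|
| 0.20 | any | 0 | 20.0% | 5.5% |
| 0.20 | 0.25 | 0.25 | 0.20 × (1 − 0.0625) = 18.8% | 6.7% |
| 0.20 | 0.50 | 0.50 | 0.20 × (1 − 0.25) = 15.0% | 12.1% |
| 0.20 | 0.75 | 1 | 0.20 × (1 − 0.75) = 5.0% | 51.3% |
| 0.40 | 0.25 | 0.25 | 0.40 × (1 − 0.0625) = 37.5% | 0.2% |
| 0.40 | 0.75 | 1 | 0.40 × (1 − 0.75) = 10.0% | 25.4% |

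The effect runs from slight to large, depending on values the protocol does not supply.

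**The case against.** The strongest reply is that the protocol, read as a whole, favours recording. The record-all sentence, the named anticipated AEs in 6.4, the unqualified acuity rule in 9.2.2 and the place given to underlying illness in 6.3.3 all point towards recording first and attributing later. The exemption covers natural progression, not every sign that also occurs in dry eye. Section 1.1 lists signs and symptoms; on course it says only that severity and prevalence rise with age. New redness in one eye within 42 days of an application is not obviously natural progression. All of this makes misuse less likely. It does not say which rule governs, and if little natural progression is expected in 42 days, the exemption has little legitimate use for these events.

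A reader might go further and infer that the exemption removes the events that make up the primary safety endpoint. It does not: seven of the ten examples have no counterpart in 1.1, and staining and acuity loss come from 6.4, not from the list in 3.2.2.

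A reader might also infer that the worsening would go undocumented and that the fellow eye could not serve as a comparator. That is not supported either. OSDI for each eye, acuity and slit-lamp findings are scheduled at Days 3, 14 and 42, and staining at baseline and Day 42 (Appendix A). Section 4.6 compares changes in OSDI and staining between device and sham eyes, and 4.7 summarises acuity and biomicroscopy at each visit. None of this depends on the AE page. What can be lost is the AE entry, its relatedness grade and the AE-level comparison between eyes.

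Finally, the protocol does not say that the investigator is unmasked, only that the participant is masked.

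**Conclusion.** The point holds in this limited form. Section 6.2 contains a causal filter that precedes relatedness grading, has no exception for the study disease, and conflicts with the record-all rule in the same section and with 6.4 and 9.2.2. It can lower the primary safety proportion through irritation, conjunctival injection and epiphora, and through staining and acuity loss if these are judged device-related.

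The size of any undercount cannot be derived, because no event rate is stated and no one can know how often the exemption would be applied. What can be said is that each participant lost from the numerator costs 7.7 points at n = 13 or 10 points at n = 10. The endpoint is per participant, so this happens only when every one of that person's device-related events is omitted. With so few participants, one or two such omissions could decide whether the study reports any device-related event. The conclusion assumes that the exemption is read as applying to dry eye disease. Its wording allows this, and no other section excludes it.

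**What to change.** Add one sentence to 6.2: the natural-progression exemption does not apply to new or worsened events, relative to baseline or Day 0, of the types listed in 3.2.2 and 6.4 in either study eye after application. Such events go on the AE page with the eye named, and attribution to dry eye disease is considered only at the relatedness step in 6.3.3. Stating that 6.4 and 9.2.2 prevail where their thresholds are met would settle the remaining conflict.

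The exemption can stay as it is for all other chronic conditions and changes, so a blanket removal for every ocular condition is not needed. The cost is one sentence, an eye field on the AE page if it lacks one, and a somewhat higher recorded ocular AE count. Visits, tests and participant care do not change.
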